### **13.4. Reporting Adverse Events**

The Investigator will notify the Sponsor of an adverse event by e-mail, facsimile, or telephone as soon as possible and no later than 24 hours from discovery for any serious /significant adverse events, and 2 days from discovery for any non-significant adverse event. In addition, a written report will be submitted by the Principal Investigator to the IEC/IRB according to their requirements (section 13.4.2). The report will comment whether the adverse event was considered to be related to the test article, study treatment or study procedures.

# **Clinical Study Protocol**

## **Johnson & Johnson Vision Care, Inc.**

### **13.4.1. Reporting Adverse Events to Sponsor**

#### **Serious/Significant Adverse Events**

The Investigator will inform the sponsor of all serious/significant adverse events occurring during the study period as soon as possible by e-mail or telephone, but no later than 24 hours following discovery of the event. The Investigator is obligated to pursue and obtain information requested by the Sponsor in addition to that information reported on the eCRF. All subjects experiencing a serious/significant adverse event must be followed up and all outcomes must be reported.

When medically necessary, the Investigator may break the randomization code to determine the identity of the treatment that the subject received. The Sponsor and study monitor should be notified prior to unmasking the test articles.

In the event of a serious/significant adverse event, the Investigator must:

- Notify the Sponsor immediately.
- Obtain and maintain in the subject's records all pertinent medical information and medical judgment for colleagues who assisted in the treatment and follow-up of the subject.
- Provide the Sponsor with a complete case history which includes a statement as to whether the event was or was not related to the use of the test article.
- Notify the IEC/IRB as required by the IEC/IRB reporting procedure according to national regulations.

#### **Unanticipated (Serious) Adverse Device Effect (UADE)**

In the event of an Unanticipated (Serious) Adverse Device Effect (UADE), the Investigator will submit a report of the UADE to the Sponsor and IEC/IRB as soon as possible, but no later than 24 hours after the Investigator first learns of the effect. This report is in addition to the immediate notification mentioned above.

The Sponsor must conduct an evaluation of the UADE and must report the results of the evaluation to FDA, the IEC/IRB and participating Investigators within 10 working days after the Sponsor first receives notification of the effect.

#### **Non-Serious Adverse Events**

All non-serious adverse events, including non-serious adverse device effects, will be reported to the sponsor by the Investigator no later than 2 days from discovery.

### **13.4.2. Reporting Adverse Events to the Responsible IEC/IRB and Health Authorities**

Adverse events that meet the IEC/IRB requirements for reporting must be reported within the IEC/IRB's written guidelines. Each clinical site will refer to and follow any guidelines set forth by their Approving IEC/IRB. Each clinical site will refer to and follow any guidelines set forth by their local governing Health Authorities.

# **Clinical Study Protocol**

## **Johnson & Johnson Vision Care, Inc.**

The Sponsor will report applicable Adverse Events to the local health authorities according the written guidelines, including reporting timelines.

### **13.5. Event of Special Interest**

None

### **13.6. Reporting of Pregnancy**

Subjects reporting pregnancy (by self-report) during the study will be discontinued after the event is recorded as an Adverse Event. Once discontinued, pregnant participants and their fetuses will not be monitored for study related purposes. Pregnant participants are not discontinued from contact lens or solution related studies for safety concerns, but due to general concerns relating to pregnancy and contact lens use. Specifically, pregnant women are discontinued due to fluctuations in refractive error and/or visual acuity that occur secondary to systemic hormonal changes, and not due to unforeseen health risks to the mother or fetus.

## **14. STATISTICAL METHODS**

### **14.1. General Considerations**

Statistical Analysis will be undertaken by the sponsor or under the authority of the sponsor. A general description of the statistical methods to be implemented in this clinical trial is outlined below. More details will be included in the stand-alone Statistical Analysis Plan (SAP). The SAP will be developed and finalized prior to database lock.

All data summaries and statistical analyses will be performed using the SAS software Version 9.4 or higher (SAS Institute, Cary, NC). Throughout the analysis of data, the results for each subject/eye will be used when available for summarization and statistical analysis. Unscheduled visits will be summarized separately and will be excluded from the statistical analysis.

Summary tables (descriptive statistics and/or frequency tables) will be provided for all baseline variables, efficacy variables and safety variables as appropriate. Continuous variables will be summarized with descriptive statistics (n, mean, standard deviation (SD), median, minimum and maximum) and will be summarized by lens type and ARM (ARM1- AO1D and ARM2 – Subjects' Habitual Lenses and AO1D) Frequency count and percentage of subjects or eyes within each category will be provided for categorical data.

### **14.2. Sample Size Justification**

This study was design and powered to demonstrate non-inferiority of the change from baseline (CFB: 2-Week Follow-up minus baseline) of the Test lens relative to subjects' habitual CLUE comfort scores, a margin of -5 points will be used to test the hypothesis. Additionally, a power analysis for the change from baseline (CFB: 2-week follow-up minus baseline) of the Test lens compared to subjects' habitual lens with respect to CLDEQ-8 total scores was also provided. Table 7 and Table 8 below displays the descriptive statistics for the CLDEQ-8 total scores and CLUE comfort scores, respectively observed from the historical data including [REDACTED],

# Clinical Study Protocol

## Johnson & Johnson Vision Care, Inc.

████████ and ██████ considering the following 5 habitual lens types: Johnson & Johnson 1-Day ACUVUE® Moist, Alcon DAILIES® Aqua Comfort Plus®, Alcon DAILIES TOTAL1®, Clariti 1-Day and MyDay. Subjects included in Table 7 had a CLDEQ-8 score of 15 or higher at screening.

Table 7 : Historical Descriptive Statistics by Study and Lens Type for CLDEQ-8 Scores

| Study    | N  | Mean (SD)   |                   |              |
|----------|----|-------------|-------------------|--------------|
|          |    | AO1D 2-week | Habitual Baseline | Difference   |
| Overall  | 24 | 12.8 (6.35) | 20.3 (4.39)       | -7.5 (7.17)  |
| ████████ | 11 | 12.5 (4.37) | 19.3 (3.13)       | -6.8 (4.77)  |
| ████████ | 5  | 13.4 (6.27) | 18.2 (4.32)       | -4.8 (8.04)  |
| ████████ | 8  | 12.9 (9.06) | 22.9 (5.11)       | -10.0 (9.30) |

Table 8 : Historical Descriptive Statistics by Study and Lens Type for CLUE Comfort Scores

| Study    | N  | Mean (SD)    |                   |               |
|----------|----|--------------|-------------------|---------------|
|          |    | AO1D 2-week  | Habitual Baseline | Difference    |
| Overall  | 24 | 52.6 (18.78) | 37.9 (18.12)      | 14.72 (25.21) |
| ████████ | 11 | 55.0 (16.18) | 38.1 (16.47)      | 16.9 (20.38)  |
| ████████ | 5  | 52.0 (19.38) | 54.8 (21.88)      | -2.8 (36.80)  |
| ████████ | 8  | 49.7 (23.48) | 27.1 (8.93)       | 22.6 (20.60)  |

Table 9 displays the sample size estimates for the primary endpoint of CLUE Comfort score, and the secondary endpoint of CLDEQ8- Scores for different scenarios of effect sizes. CLDEQ-8 power analysis was provided for informational purposes. All Sample size calculations were performed with 80% power and 2-sided alpha=0.05. With respect to CLDEQ-8 Scores, for ARM1 a standard deviation of 7.17 was utilized (See Table 7 ), while a standard deviation of 5.0 was utilized for ARM2 in each calculation for the various effect sizes. The different effect sizes for CLDEQ-8 scores were based on the historical effect sizes provided in Table 7. Historically, on average AO1D improved CLEQ8-scores about 7 points after 2-weeks of wear. The power analysis for CLDEQ8-scores is displayed in Table 9 below. With respect to CLUE comfort scores, for ARM1 a standard deviation of 25.21 was used (See Table 8) while, a standard deviation of 18.12 was utilized for ARM2 in the calculation for each scenario. Due to the varying effect sizes displayed in Table 8 above, effect sizes of 3, 5 and 9 were utilized as a more conservative estimate for the sample size calculation since there was a high a difference observed between AO1D and subjects' habitual lenses with respect to CLUE Comfort (22.6 points) in ██████.

Sample size and power calculations for each endpoint and scenario were calculated using a 2-sided Satterthwaite t-test assuming unequal variances using the POWER^11 procedure in SAS Version 9.4.

**Clinical Study Protocol**  
**Johnson & Johnson Vision Care, Inc.**

Table 9 : Sample Size Calculation and Power Analysis required to Test Primary Hypothesis for CLUE Comfort and Secondary hypothesis for CLDEQ8-scores for different Scenarios of Effect Sizes

| Endpoint                      | Endpoint Type | Power | Standard Deviation          | Effect Size | Sample Size per Arm | Total Sample Size (Including dropout rate) |
|-------------------------------|---------------|-------|-----------------------------|-------------|---------------------|--|
| Change in CLUE Comfort Scores | Primary       | 80%   | ARM1- 25.21
ARM2 – 18.12 | 3           | 120                 | 336  |
|                               |               |       |                             | 5           | 77                  | 216  |
|                               |               |       |                             | 9           | 40                  | 112  |
| Change in CLDEQ-8 Scores      | Secondary     | 80%   | ARM1- 7.17
ARM2- 5.00    | -3          | 68                  | 190  |
|                               |               |       |                             | -4          | 39                  | 110  |
|                               |               |       |                             | -5          | 26                  | 72   |

Table 10 contains subject accountability by status for each historical study. As indicated below a total of 65 subjects either failed to meet all eligibility criteria or were discontinued from the study. Based on the information provided in the table below a ~24% ( $\frac{65}{265} = 0.245$ ) was observed in the historical studies. However, due to the ongoing Pandemic of COVID-19 and the stringent enrollment for the 5 habitual lens types, to account for a high number dropouts or screen failures ~40% increase in enrollment is necessary to meet our target subject completion number.

Table 10: Subject Accountability Status by Study

| Study      | Number Enrolled | Number Assigned not dispensed | Number Screen Failed | Number Dispensed | Number Completed | Number Discontinued |
|------------|-----------------|-------------------------------|----------------------|------------------|------------------|---------------------|
| ██████████ | 105             | 1                             | 23                   | 81               | 73               | 8                   |
| ██████████ | 58              | 0                             | 9                    | 49               | 39               | 10                  |
| ██████████ | 102             | 0                             | 10                   | 92               | 87               | 5                   |
| Total      | 265             | 1                             | 42                   | 222              | 199              | 23                  |

It was determined that a total of 112 subjects will be sufficiently large enough to demonstrate non-inferiority the Test lens compared to subjects' habitual lens with respect to the change in CLUE Comfort scores from baseline to 2-week follow-up considering a ~40% dropout/screen failure rate.

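### Section 14.2 says 112 enrolled covers about 40% loss, but 112 yields 80 completers only up to 28.6% loss; Table 9's CLDEQ-8 rows leave out the margin of the hypothesis they are labelled for

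*Combined protocol and SAP*

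**What the plan says.** The Synopsis and sections 3.1 and 4.3 plan for about 112 enrolled and about 80 completers, 40 in each arm. Section 4.3 counts a subject as enrolled at informed consent.

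Section 14.2 describes the step from 80 to 112 in three ways:

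- Below Table 9, after reporting a historical loss of about 24%, it says a "40% increase in enrollment is necessary to meet our target subject completion number". It gives COVID-19 and the restriction to five habitual lens types as reasons to expect more loss than before.
- The last column of Table 9 is headed "Total Sample Size (Including dropout rate".
- The closing sentence of the section finds 112 sufficient "considering a ~40% dropout/screen failure rate".

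Table 9's title says its figures are those "required to Test Primary Hypothesis for CLUE Comfort and Secondary hypothesis for CLDEQ8-scores". For CLUE, section 14.2 says "a margin of -5 points will be used to test the hypothesis". It states no margin for CLDEQ-8, although sections 2.3 and 14.6 define that secondary hypothesis as non-inferiority with a margin of 3 points. Section 14.2 adds that the "CLDEQ-8 power analysis was provided for informational purposes".

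**The concern.** A 40% increase over the completer target and a 40% loss from the enrolled number are different quantities. The closing sentence is where the plan says enrolment suffices, and it names a loss rate that 112 may not cover. The section itself expects loss above the historical level, so the range just above 25% is the one that matters. Anyone tracking accrual against a 40% tolerance would see no warning until well after the completion target was out of reach.

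The CLDEQ-8 rows raise a smaller question. If the CLUE rows contain their margin and the CLDEQ-8 rows do not, one table mixes two kinds of test under one title. A reader would then conclude that 40 per arm is too few for the CLDEQ-8 hypothesis at an effect of -3, where the table asks for 68.

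**Working it through.** **Inputs (section 14.2).** Two-sided alpha 0.05, 80% power, Satterthwaite t-test, equal arms. CLUE change: SD 25.21 in ARM 1 and 18.12 in ARM 2, effects 3, 5 and 9, margin 5. CLDEQ-8 change: SD 7.17 in ARM 1; for ARM 2, "a standard deviation of 5.0 was utilized for ARM2 in each calculation for the various effect sizes", with no source given; effects -3, -4 and -5. The CLDEQ-8 margin of 3 comes from section 2.3.

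**Step 1: reproduce n per arm.** Let the distance be the effect plus the margin, if a margin is used. The noncentrality is distance / sqrt((s1² + s2²)/n). For CLUE at effect 9: 14 / sqrt((25.21² + 18.12²)/40) = 14 / 4.91 = 2.85, which gives power 80.3%.

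| Row | Table 9 | With margin | Without margin |
|---|---|---|---|
| CLUE, effects 3 / 5 / 9 | 120 / 77 / 40 | 120 / 77 / 40 | 842 / 304 / 95 |
| CLDEQ-8, effects -3 / -4 / -5 | 68 / 39 / 26 | 18 / 14 / 11 | 68 / 39 / 26 |

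The CLUE rows include their margin. The CLDEQ-8 rows do not, so they size a superiority test. At 40 per arm on the stated SDs, CLDEQ-8 non-inferiority power is 99.0%, 99.9% and over 99.9% for effects -3, -4 and -5; superiority power is 57%, 81% and 95%. If 7.17 is assumed in both arms, the rows with margin are 24, 18 and 14.

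**Step 2: reproduce the totals.** 2 × round(1.4 × n) for n = 120, 77, 40, 68, 39, 26 gives 336, 216, 112, 190, 110, 72, all six as printed. Dividing 2n by (1 - 0.40) instead gives 400, 257, 134, 227, 130, 87, and none matches.

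**Step 3: what 112 tolerates.**

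- Largest loss that still leaves 80 completers: 1 - 80/112 = 28.6%.
- Enrolment needed at 40% loss: 80/0.60 = 133.3, so 134.
- Completers from 112 at 40% loss: 112 × 0.60 = 67.2.
- Historical loss: 65/265 = 24.5% as stated. Table 10 gives 42 + 1 + 23 = 66 = 265 - 199, so 66/265 = 24.9%. At that yield, 112 × 199/265 = 84 completers.

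**Step 4: power at 40% loss (CLUE, effect 9).** With no replacement and equal loss, 33 or 34 complete per arm, and power is 72.1% or 73.4%.

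Now suppose each discontinued subject is replaced by one new enrolment and screen failures are not replaced. Assume losses split as in Table 10, with 23 or 24 of 66 after dispensing. The one subject assigned but not dispensed can be counted either way.

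- Enrolled: 112 / (1 - 0.4 × 23/66) = 130.1, or 112 / (1 - 0.4 × 24/66) = 131.1.
- Completers: 0.6 × 130.1 = 78.1, or 0.6 × 131.1 = 78.6. That is about 39 per arm, with power 79.3%.

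**Taken as given.** On the ARM 2 CLUE value, section 14.2 says "a standard deviation of 18.12 was utilized for ARM2 in the calculation for each scenario". In Table 8 that figure is the SD of the habitual baseline score, not of a change. It equals a change SD only if the baseline to follow-up correlation is s/(2 × 18.12), where s is the follow-up SD, which is 0.5 when the variances are equal. True power could lie on either side of 80%. Nothing here depends on it.

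**The case against.** The strongest reply is that the derivation is disclosed. The paragraph below Table 9 correctly calls the 40% an increase, and several sections give 112 and 80 side by side. On this view the closing sentence is only loose wording. Replacement also softens the effect: section 8.2 says an additional subject will be enrolled after a premature discontinuation, and sections 4.3 and 5.2 allow replacement. The 72-73% figure, which assumes none, is therefore a worst case, and with replacement the cost is about one percentage point of power. All of that stands.

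It does not make the sentence true. 28.6% is not about 40%, and replacing subjects means enrolling more than 112. None of the replacement provisions mentions screen failures, which were 42 of the 66 historical losses. The word discontinued could be read more widely, since step 1.14 in section 7.2 uses it for a subject who fails the baseline slit lamp criterion. If some screen failures were then replaceable, 78-79 completers would be too low an estimate, but enrolment would go still further beyond 112.

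On CLDEQ-8, the rows are informational, did not set the sample size and overstate what the non-inferiority test needs. Section 14.6 also plans a superiority test, so the figures answer a planned question. That leaves a wrong label and no harm to the trial's size.

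**Conclusion.** The point holds. The claim that 112 suffices at about 40% loss is wrong as written and conflicts with the correct description in the same section. The tolerance is 28.6% before replacement, and 40% loss would need 134 enrolled. The size of 40 completers per arm is right on the stated inputs, and 112 covers loss at the historical rate.

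The consequence for power is limited: about 79% at 40% loss if discontinued subjects are replaced and losses split as in Table 10, and about 72-73% with no replacement and equal loss between arms. The allowance must also absorb two things the section does not mention. The primary analysis is Per-Protocol (sections 14.3 and 14.5), while 80 counts completers. Step 2.5 of ARM 2 Visit 2 discontinues subjects whose CLDEQ-8 score is no longer 15 or more, a loss that arises in one arm only.

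The CLDEQ-8 rows are mislabelled. They size superiority, and the non-inferiority test they are titled for needs 18, 14 and 11 per arm on the stated SDs.

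**What to change.** In section 14.2:

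1. Reword the closing sentence to say that 112 enrolled, a 40% increase over 80 completers, allows about 28.6% screen failure plus dropout before replacement. If the sponsor does expect 40% loss, the matching figure is 134.
2. Rename the last column of Table 9 to show the rule used: 2 × (1.4 × n per arm, rounded).
3. Add that 80 counts completers, so Per-Protocol exclusions and unequal loss between arms come out of the same allowance.
4. Label the CLDEQ-8 rows as sizing the superiority test of section 14.6, or recompute them with the margin of 3 (18, 14, 11 on SDs 7.17 and 5.0). Give the source of the 5.0 in either case.

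Restating the tolerance changes only text and table labels in section 14.2; enrolment, visits and analysis stay as they are.

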# **Clinical Study Protocol**

## **Johnson & Johnson Vision Care, Inc.**

### **14.3. Analysis Populations**

#### **Safety Population:**

All subjects who are administered any test article excluding subjects who drop out prior to administering any test article. At least one observation should be recorded.

#### **Per-Protocol Population:**

All subjects who successfully complete all visits and do not substantially deviate from the protocol as determined by the trial cohort review committee prior to database hard lock. Justification for the exclusion of subjects with protocol deviations from the per-protocol population set will be documented in a memo to file.

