## **4. STUDY DESIGN AND RATIONALE**

### **4.1. Description of Study Design**

This is a multi-site, randomized, bilateral, dispensing, parallel design study with two arms (ARM 1 and ARM 2). Subjects will be pre-screened for contact lens related dryness symptoms via phone or email prior to enter the study.

Subjects in ARM 1 will be fitted into AO1D and followed up after 2 weeks of wear. Subjects will be masked to the identity of the lens assigned. There will be 2 visits as follows:

- Pre-screen questions via. phone or email
- Visit 1: Screening, baseline evaluation, fitting AO1D
- Visit 2: 2-week follow up and final evaluation

Subjects in ARM 2 will be first fitted into their habitual lenses and dispensed for 2 weeks. At the follow-up visit, subject will be fitted into AO1D and followed up after 2 weeks of where. Subjects will not be masked to their habitual lens (open label), but they will be masked to the identity of AO1D during the second period of wear. There will be 3 visits as follows:

- Pre-screen questions via phone or email
- Visit 1: Screening, baseline evaluation, fitting habitual lens
- Visit 2: 2-week habitual lens follow up; fitting AO1D
- Visit 3: 2-week AO1D follow up and final evaluation

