### **5.3. Procedures for Maintaining and Breaking the Masking**

One randomization code (alphanumeric character) per test article will be assigned by the study biostatistician using the form [REDACTED]. For ARM 2, one randomization code will be used for subjects' habitual lens regardless of the lens brand and type. Upon database lock, the study biostatistician will release the randomization codes to the data management.

When dispensing test articles, the following steps should be followed:

1. Investigator or designee (documented on the Delegation Log) will consult the lens fitting schedule/randomization scheme to obtain the test article assignment for that subject prior to dispensing.
2. Investigator or designee will record the subject's number on the appropriate line of the randomization scheme.
3. Investigator or designee will pull the appropriate test articles from the study supply. All test articles that are opened, whether dispensed (placed/fit on eye or dispensed outside the clinical site) or not, must be recorded on the Test Article Accountability Log in the "Dispensed" section.

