### **14.5. Primary Analysis**

The primary endpoint is the change in CLUE comfort score from baseline to 2-week follow-up. The data from the ARM 1 (Test) will be compared to the first period of the ARM 2 (Control, habitual lens). The primary analyses will be conducted on the Per-Protocol (PP) population. A sensitivity analysis will be conducted on the Intent-to-Treat (ITT) population. Non-inferiority will be assessed on PP population, while superiority will be assessed on ITT population.

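### The Per-Protocol set that alone decides non-inferiority has no fixed deviation rule and no stated masking of the committee that applies it, and it makes ARM 2 membership depend on a visit the primary comparison does not use

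*Combined protocol and SAP*

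**What the plan says.** Section 14.5 gives the deciding role to one population: "Non-inferiority will be assessed on PP population, while superiority will be assessed on ITT population". ITT has a supporting role for the primary claim: "A sensitivity analysis will be conducted on the Intent-to-Treat (ITT) population". No rule says how a disagreement between the two would be read.

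Section 14.3 sets two conditions for the Per-Protocol set. The subject must finish every visit, and must "do not substantially deviate from the protocol as determined by the trial cohort review committee prior to database hard lock". Reasons for exclusion go into a memo to file. Section 10 (Table 6) gives examples of major and minor deviations, but Section 14.3 does not refer to them.

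Section 5.3 holds back the codes: "Upon database lock, the study biostatistician will release the randomization codes to the data management". Section 5.2 masks only subjects, and only to the Test lens.

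Section 4.1 gives ARM 1 two visits and ARM 2 three. The last one, "Visit 3: 2-week AO1D follow up and final evaluation", exists only in ARM 2, as does the preference questionnaire (Table 3). Section 14.5 compares ARM 1 with the first period of ARM 2 only, and that period ends at Visit 2. Section 7.2, ARM 2 Visit 2, Step 2.5 discontinues ARM 2 subjects whose CLDEQ-8 score no longer reaches 15.

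On timing, Section 14.1 says: "The SAP will be developed and finalized prior to database lock".

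**The concern.** There are two separate problems.

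The first is discretion. A committee decides which deviations count, with no closed list. Holding the codes until lock does not mask that step, because whether a subject has finished every visit cannot be checked without knowing whether two or three visits were due. Section 16.4 says that masking is kept in the data prepared for the Data Monitoring Committee. Nothing comparable is said for the cohort review committee, and nothing says that it works without questionnaire scores.

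The second problem needs no assumption about how the committee behaves. Visit 3 plays no part in the primary comparison, yet an ARM 2 subject who misses it leaves the Per-Protocol set. Step 2.5 sends one group out before Visit 3 because of a Visit 2 symptom score. Membership therefore depends on arm and on outcome.

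At stake is the test on which the study objective rests (Section 2.3), in a trial meant to support market claims.

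**Working it through.** **The plan's own figure.** Inputs from Section 14.2 and Table 9: SD 25.21 (ARM 1) and 18.12 (ARM 2), assumed effect 9, margin −5, two-sided alpha 0.05, 80% power. A Satterthwaite t-test with shift 9 + 5 = 14 gives 40 per arm (power 80.3%). Effects 3 and 5 give 120 and 77. All three match Table 9, and 80 × 1.4 = 112 matches the enrolment target. This point does not rest on a sample size error.

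**Precision.** SE = √((25.21² + 18.12²)/40) = √(963.9/40) = 4.9 points.

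**Shift from chosen exclusions.** If *k* of 40 subjects are removed and they lie on average *d* points below the arm mean, the mean of the rest rises by *k·d*/(40 − *k*). A simulation (40,000 runs, normal data, the SDs above, true difference at −5, 95% Satterthwaite interval) removed the *k* lowest ARM 1 values:

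| ARM 1 subjects removed | Average difference | Shift | One-sided type I error |
|---|---|---|---|
| 0 | −5.02 | – | 2.4% |
| 1, lowest | −3.63 | 1.4 | 5.1% |
| 2, lowest | −2.43 | 2.6 | 8.8% |
| 3, lowest | −1.33 | 3.7 | 13.4% |
| 1, 2 or 4, at random | −5.02 to −5.03 | none | 2.4% |

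For *k* = 2 the formula returns *d* = 2.59 × 38/2 = 49 points, about 1.95 SD. The shift of 2.6 is 52% of the margin. Exclusions unrelated to outcome cost only power: 80.3% at 40 per arm, 75.9% at 36 per arm.

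**The visit condition.** Take two subjects, each with CLDEQ-8 below 15 at Visit 2 and no other deviation:

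| | ARM 1 | ARM 2 |
|---|---|---|
| Used in the primary comparison | Baseline, Visit 2 | Baseline, Visit 2 |
| Effect of the score | None; study completed | Discontinued (Step 2.5) |
| Every visit finished | Yes | No, Visit 3 missed |
| In the Per-Protocol set | Yes | No |

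The ARM 2 subjects lost are those whose symptoms improved on the habitual lens. If CLUE comfort moves with CLDEQ-8 (an assumption; the documents give no correlation), losing them lowers the control change and favours the Test lens. The documents do not give the number affected. For scale, removing the 1 to 4 highest ARM 2 values in the same simulation shifts the difference by 1.0 to 3.4 points. For a given number that is an outer limit, since Step 2.5 selects on CLDEQ-8 and not on CLUE.

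It is also unclear whether these subjects have a Visit 2 CLUE score. Step 2.5 sends them straight to the final evaluation, ahead of the CLUE form at Step 2.6, while Section 8.2 asks that the current visit be completed.

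**The missing threshold.** Section 7.2 (Step 1.26) requires at least 10 days of wear at 8 hours. Table 6 calls wear a major deviation when it falls short of 6 hours on 5 days. Section 8.2 withdraws subjects who do not comply with the wear schedule. A subject with 9 days at 7 hours misses the first, passes the second, and may or may not be caught by the third. Section 14.3 does not say which applies.

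**The case against.** The strongest reply is that the plan already contains controls. Table 6 describes major deviations for visit windows, blank questionnaire items and wear. Section 10 has deviations reported within 24 hours and tracked, and prohibits waivers. Section 14.3 allows exclusion for missed visits or deviations, not for a poor score. The ITT analysis would show a selective exclusion as a gap between the two results. Sections 14.5 and 14.10 already fix the endpoint, model terms, margin and interval rule, and require changes to be justified in the report, so a late SAP leaves open mainly covariates such as age and gender and the covariance structure.

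Much of this stands. SAP timing alone would be a small matter. But Table 6 is a set of examples that Section 14.3 does not invoke, and no rule gives ITT any weight if it disagrees. ITT can retain the ARM 2 subjects discontinued at Visit 2 only if their CLUE score was collected.

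A reader might infer that the committee sees comfort scores when it decides. The documents do not support that: they give neither its membership nor its data access. Knowledge of arm is a fair inference from the visit structure; knowledge of scores is not. What can be said is that masking to either is not stated.

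**Conclusion.** The concern holds as a gap in the rule, not as evidence of biased selection. Three things rest directly on the text: non-inferiority is decided on the Per-Protocol set, the deviation threshold is left to a committee whose masking is not described, and ARM 2 membership in the primary comparison depends on Visit 3 and, through Step 2.5, on a Visit 2 score. Section 7.2 (Step 2.5), Section 14.3 and Section 14.5 must be reconciled.

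The 2.6-point shift and the rise in type I error from 2.4% to 8.8% are a worst-case bound. They assume normal data, 40 per arm, and that the two lowest ARM 1 scorers are the ones excluded. Reading them as the expected bias would be wrong: exclusions unrelated to outcome leave the error at 2.4%. They show only that, with a standard error of 4.9, a few exclusions matter. The size of the Step 2.5 effect cannot be fixed from the documents.

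**What to change.** 1. In Section 14.3, define the Per-Protocol set for the between-arm tests by completion up to Visit 2 and a closed list of major deviations of the Table 6 kind occurring up to Visit 2. Define a separate set, using Visit 3, for the two within-ARM 2 secondary tests (Section 14.6). Reconcile the wear thresholds in Sections 7.2, 8.2 and 10, and state whether subjects discontinued at Step 2.5 complete the CLUE form.
2. Let the committee rule only on deviations not on the list, from listings without arm identifiers or questionnaire scores and, for the between-arm set, without Visit 3 data. Blank questionnaire items can be shown as counts.
3. In Section 14.1, require the SAP to be signed before that review begins.

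The cost is protocol and SAP wording, one masked listing program and slightly earlier SAP work. No additional subjects are needed.
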